COMIRB PROTOCOL #: 14-0909

PROTOCOL VERSION: April 27, 2018

PROTOCOL TITLE: An open label, randomized, Phase II trial of Metabolic complications in patients treated with enzalutamide vs standard ADT for the treatment of hormone sensitive prostate cancer

NCT02278185

COORDINATING CENTER: *University of Colorado Cancer Center*

LEAD PRINCIPAL INVESTIGATOR: *[name]*

University of Colorado Denver, Division of Medical Oncology

[name]

[name]

[contact]

[contact]

[contact]

Statistician:

[name]

Protocol Summary

An open label, randomized, Phase II trial of Metabolic complications in patients treated with enzalutamide vs standard ADT for the treatment of hormone sensitive prostate cancer	
Primary Objective	To determine the incidence of metabolic syndrome within 12 months, as defined by the Adult Treatment Panel III, in patients treated with enzalutamide compared to standard androgen deprivation therapy.
Secondary Objectives	In patients on enzalutamide versus traditional ADT: 
  To determine the incidence of metabolic syndrome within 6 months, as defined by the Adult Treatment Panel III, in patients treated with enzalutamide compared to standard androgen deprivation therapy.  To assess bone health, as measured by a DXA scanner  To assess body composition (sarcopenic obesity), as measured by cross sectional CT analysis  To assess QOL, as measured by the FACT-P and SHIM  To assess time to PSA progression and time to radiographic progression. Progression will be defined as lack of clinical benefit in the setting of either rising PSA, growth of visceral or soft tissue metastasis, or development of new bone metastasis as defined per protocol  To assess the incidence of developing individual risk factors, or components, which comprise metabolic syndrome  To assess the safety and tolerance of enzalutamide or ADT  To assess the change in hs-CRP as a marker of inflammation  To assess the change in physical function as measured by the Short Physical Performance Battery
Study Population	Patients with biochemically recurrent disease, metastatic disease, and patients offered ADT as primary therapy if they are not candidates for local therapy.
Other Participating Site (enrolling subjects)	University of Colorado Health - Poudre Valley Hospital (UCH-North) Site Principal Investigator: [name]
STUDY DESIGN	
Multi-center, open label, randomized, phase II trial evaluating the incidence of metabolic syndrome within 12 months in patients treated with enzalutamide in comparison with androgen deprivation therapy for treatment of advanced prostate cancer. Enzalutamide 160mg orally daily versus standard androgen deprivation therapy. Acceptable forms of ADT will be specified and this therapy must result in castrate levels of testosterone. Patients will be treated for a 12-month period and assessed for the development of metabolic syndrome at 3 month intervals. Patients with continued clinical benefit beyond the 12-month endpoint may continue on their assigned treatment through standard of care prescribing methods.	

TABLE 1: Schedule of Events	Screening Day 0	Start of Treatment Month 1, Day1 ²	Month 2, Day1	Month 4, Day 1	Month 7, Day 1	Month 10, Day 1	Month 13, Day 1 End of Treatment	End of study ⁶
Informed Consent	X							
VISIT ASSESSMENTS								
Adverse events assessment	X	X	X	X	X	X	X	X
Review medication list	X	X	X	X	X	X	X	X
Physical Exam and history	X	X	X	X	X	X	X	X
Vital signs, including weight, waist circumference	X	X	X	X	X	X	X	X
Height	X							
Performance Status	X	X	X	X	X	X	X	X
LABORATORY STUDIES								
CBC, Comprehensive metabolic panel (fasting for glucose)	X ¹	X	X	X	X	X	X	X ⁸
PSA	X	X ⁷	X	X	X	X	X	
Lipid Profile (including triglycerides and HDL)	X			X	X	X	X	
N-Telopeptide, Bone specific alkaline phosphatase, hs-CRP, estradiol		X		X	X	X	X	
Testosterone	X		X	X	X	X	X	
25-OH Vitamin D	X				X		X	
IMAGING								
Fill out QOL questionnaires (FACT – P and SHIM)		X		X	X	X	X	
Bone densometry (DXA)		X ⁹		X				X ⁹
CT scan of chest, abdomen, pelvis ^{3, 4}	X				X		X	
Nuclear Bone scan ^{3,4}	X				X		X	
TREATMENT								
Enzalutamide dosed at 160mg po daily		X	X	X	X	X		
GNRH agonist/antagonist (Standard of care)		X	X	X	X	X		
Calcium/Vitamin D ⁵		X	X	X	X	X		
OTHER								
Short physical performance battery		X		X	X	X	X	
Optional biomarker blood testing (3 tubes, see lab manual)		X		X	X	X	X	

1 May be performed from day -14 to 0. Screening is day 0.

2 Day 1 Month 1 must occur with 21 days of screening. Visit days of the remaining months must occur +/- 5 days to date on the calendar.

3 May be performed Day - 28 - Day 0

C _{max}	Maximum plasma concentration
CT	Computed tomography
CTCAE	Common Terminology Criteria for Adverse Events
CYP	Cytochrome P ₄₅₀
DDI	Drug-drug interaction
DNA	Deoxyribonucleic acid
DXA	Dual-energy x-ray absorptiometry scan
ECG	Electrocardiogram
ECOG	Eastern Cooperative Oncology Group
EOS	End of study
FACT-P	Functional assessment of cancer therapy-prostate
FDA	Food and Drug Administration
FPG	Fasting plasma glucose
FSH	Follicle stimulating hormone
GABA	Gamma-aminobutyric acid
GnRH	Gonadotropin releasing hormone
GCP	Good Clinical Practice
GLP	Good Laboratory Practices
HDL	High density lipoprotein
HIPAA	Health insurance portability and accountability act
HR	Hazard ratio

COMIRB/Protocol # 14-0909**Protocol Version:****4.27.2018 PI: [name]**

Abbreviation	Term
IB	Investigator's Brochure
ICF	Informed Consent Form
ICH	International Conference on Harmonisation
IEC	Independent Ethics Committee
IND	Investigational new drug
IRB	Institutional Review Board
IU	International units
LDL	Low density lipoprotein
LH	Leutinizing hormone
LHRH	Leutinizing hormone releasing hormone
MedDRA	Medical Dictionary for Regulatory Activities
MTD	Maximum tolerated dose
NCI	National Cancer Institute
NCI CTCAE	National Cancer Institute Common Terminology Criteria for Adverse
NYHA	New York Heart Association
PI	Principal investigator
PD	Progressive disease
PFS	Progression-free survival
PSA	Prostate specific antigen
PCWG2	Prostate Cancer Working Group 2
QOL	Quality of life
RECIST	Response Evaluation Criteria in Solid Tumors
SAE	Serious adverse event
SPPB	Short physical performance battery
SRE	Skeletal related event
SUSAR	Serious Unexpected Suspect Adverse Reaction
SHIM	Sexual Health Inventory in Men
T _{1/2}	Terminal half life
UCH-North	University of Colorado Health – Poudre Valley Hospital
ULN	Upper limit of the normal range
V/F	Volume of distribution
WHO	World Health Organization

1. BACKGROUND AND STUDY RATIONALE

1.1 Prostate cancer

Prostate cancer is the most common non-cutaneous cancer in men in the United States, and the second leading cause of cancer death in US men¹. As many as three-quarters of prostate cancer patients present with localized disease yet a good proportion have recurrent or metastatic disease requiring systemic treatment with androgen deprivation therapy (ADT).

1.2 Androgen deprivation therapy and metabolic syndrome

While many new agents have been developed for the treatment of prostate cancer, these focus on treatment in the metastatic, castrate-resistant setting. Patients requiring systemic therapy for prostate cancer continue to be initially treated with traditional gonadotropin hormone analogues, despite advances in therapeutic development. The treatment is very effective with survival results mainly impacted by disease state at initiation. The average time from biochemical recurrence, or prostate specific antigen (PSA) relapse, to development of metastatic disease is approximately 8 years² and survival for patients with metastatic disease on ADT is approximately 30 months. The median time of response for patients with biochemically relapsed disease treated with ADT is 10.8 months³. Thereafter, patients remain on ADT in combination with other therapies for the duration of their anti-cancer therapy, which may be years. Men treated with ADT experience long-term adverse effects such as fatigue, loss of muscle mass (i.e. sarcopenia), loss of bone density, increased adiposity, development of metabolic syndrome, depression, sexual dysfunction and poor quality of life (QOL)⁴⁻¹³. Men treated with ADT had lower levels of self-reported physical function and QOL in comparison to age-matched controls^{8,10,14-17}. These effects are profound for any patients but may be felt to a larger degree in the standard older patient population afflicted with prostate cancer, already dealing with the changes of decreasing functional reserve.

1.3 Metabolic syndrome

One of the long term sequelae of ADT is the development of metabolic syndrome. While many definitions exist, “metabolic syndrome” broadly encompasses reduced insulin sensitivity and increasing body mass. The syndrome itself imposes a higher risk of cardiovascular disease and diabetes which subsequently impact mortality risk¹⁸. Metabolic syndrome is a common health problem in the United States with a distant evaluation of the prevalence estimated at over 40% for persons over the age of 60 with more recent updates suggesting that the incidence is increasing¹⁹. This is the same age group most likely to be affected by prostate cancer. A long term hypogonadal state, such as is induced by prostate cancer therapy, has been shown to independently predict the development of metabolic syndrome, and patients with metabolic syndrome have a 3 times greater risk of death from cardiovascular disease than healthy counterparts^{20,21}. There are data supporting the role of hypogonadism in independently increasing the risk of many of the components of metabolic syndrome such as dyslipidemia, hypertension, alterations in body mass and glucose intolerance, and that these parameters may change as early as 3-6 months after the initiation of therapy^{7,22-25}. Population-based analyses have shown a higher incidence of diabetes and coronary disease in patients treated with ADT^{26,27}. Cross sectional studies have shown that men with prostate cancer treated with ADT are twice as likely to meet the criteria for metabolic syndrome in comparison to matched prostate cancer patients or healthy controls⁷. Unlike many cancer treatments, patients remain on ADT for years, allowing for the development of long-term sequelae, which impact a patient’s global health and quality of life during survivorship and may contribute to overall mortality in equal parts as the cancer.

1.4 Rationale for study design

Improved understanding of the biology of prostate cancer has allowed for the development of agents, which more effectively manipulate the androgen axis even under castrate conditions. Not only reduction in circulating testosterone, but also improved blockade of the androgen receptor has led to an improvement in survival for patients with metastatic castrate resistant prostate cancer (CRPC). The development of a new generation of agents, such as enzalutamide, that preserve circulating testosterone levels while acting on the androgen receptor, provide new therapeutic opportunities for an active single agent with the potential for a reduction of the long term effects associated with ADT. Single agent data of enzalutamide reveals an excellent PSA response and tolerance profile²⁸. Preservation of these hormone levels may delay the adverse effects associated with long term ADT that contribute to development of metabolic syndrome.

The influence of the adverse events associated with newer agents on a patient's QOL is increasingly used to guide cancer care²⁹, and understanding the comparative effectiveness of agents is important. Men with prostate cancer have higher rates of noncancerous mortality than men in the general population, perhaps due to the contribution of the hypogonadal state in worsening common causes of death such as heart disease and diabetes. The clustering of cardiovascular risk factors, which occurs with ADT, may not be found in patients treated with enzalutamide due to its preservation of systemic testosterone levels. There has not been a longitudinal analysis of the development of metabolic syndrome in patients on ADT, nor a structured evaluation of the development of metabolic syndrome, or metabolic changes in patients treated with enzalutamide. This protocol will evaluate the effect of androgen blockade via enzalutamide versus traditional ADT on development of metabolic syndrome, changes in body composition, changes in quality of life, and changes in physical function in patients with advanced prostate cancer.

1.5 Enzalutamide

Enzalutamide is a non-steroidal anti-androgen that blocks the ability of testosterone to signal through the androgen receptor. Enzalutamide has no known agonistic properties even when the androgen receptor is overexpressed as supported in preclinical models of CRPC. Enzalutamide is currently approved by the FDA for treatment of men with metastatic prostate cancer that have previously been treated with docetaxel chemotherapy. In the AFFIRM trial, which led to this approval, patients received enzalutamide 160mg/day orally or placebo³⁰. The study showed a survival advantage for patients treated with enzalutamide of 18.4 months in comparison to 13.6-months (hazard ratio (HR) 0.631 [95% CI: 0.529-0.752], p< 0.0001). Other endpoints of radiographic progression free survival (PFS), 8.3 versus (vs) 2.9 months; hazard ratio (HR) 0.40, p< 0.001 and PSA response 54% vs 2%, p< 0.001 were also significantly improved in those receiving enzalutamide. The AFFIRM trial also supported an improved QOL in the enzalutamide treated group as well as improvement in time to first skeletal-related event (SRE) (16.7 vs 13.3 months; HR 0.69, p< 0.001). In addition, the PREVAIL trial is studying enzalutamide versus placebo in men with metastatic castrate resistant prostate cancer that have not yet been treated with chemotherapy and has reported promising results that will likely lead to its approval³¹.

Ongoing studies of enzalutamide are evaluating its efficacy earlier in the treatment spectrum. The Phase II, STRIVE trial is evaluating the efficacy of enzalutamide for patients that may have castrate resistant disease with metastatic and non-metastatic CRPC (NCT01664923). In addition, there was a relatively small phase II trial evaluating the use of enzalutamide prior to the initiation of traditional testosterone-lowering agents³². This single agent trial was conducted in 67 men without previous exposure to ADT with a primary endpoint of PSA response defined as an 80% decline from baseline. Monotherapy with enzalutamide was highly effective, with a median PSA decrease of 99.6% seen,

and 92.5% of patients achieving the primary endpoint at week 25. The trial enrolled patients with and without metastatic disease at baseline.

In the randomized clinical trial in patients with metastatic castration-resistant prostate cancer who had previously received docetaxel, 1200 patients were enrolled. The most common adverse drug reactions ($\geq 5\%$) reported in patients receiving enzalutamide in the randomized clinical trial were asthenia/fatigue, back pain, diarrhea, arthralgia, hot flush, peripheral edema, musculoskeletal pain, headache, upper respiratory infection, muscular weakness, dizziness, insomnia, lower respiratory infection, spinal cord compression and cauda equina syndrome, hematuria, paresthesia, anxiety, and hypertension ³³. Severe, grade ≥ 3 adverse events, were reported in 47% patients receiving enzalutamide and 53% of patients receiving placebo. The most common adverse reaction leading to treatment discontinuation in the enzalutamide treated group was seizure, which occurred in 0.9% of the enzalutamide-treated patients compared to none (0%) of the placebo-treated patients. In the Phase III trial, 7 of 800 patients treated with enzalutamide experienced a seizure in comparison to 0 events in the placebo arm. The seizures occurred days 31-603 after drug initiation. No further seizures occurred after patients discontinued enzalutamide. Patients were never readministered enzalutamide while on study, and patients with a history of seizure have been excluded in additional studies. It is thought that the mechanism of seizure may be the inhibition of the GABA-gated chloride channel. It is suggested that enzalutamide may lower the seizure threshold but not directly contribute to these events. This trial will exclude patients with a predisposition to seizure, as the exclusion of this subset of patients should not have a known impact on altering the incidence of metabolic syndrome. Another notable adverse event associated with the enzalutamide treatment arm is fall and fall-related injuries. This occurred in 4.6% of patients enrolled in the randomized trial and assigned to the enzalutamide treatment group in comparison to 1.3% of patients treated with placebo. The mechanism of fall is not clear. Fall-related injuries are described as joint injuries, non-pathologic fractures, and hematomas.

Very few laboratory abnormalities were seen in patients treated with enzalutamide. Neutropenia of all grades occurred in 15% of patients on enzalutamide (1% Grade 3-4). The incidence of thrombocytopenia was similar in the treatment and placebo arms (0.5% on enzalutamide v 1% on placebo). Elevation in transaminases occurred in 10% of patients on enzalutamide (0.3% Grade 3-4) and 18% of patients on placebo (0.5% Grade 3-4), with elevations in bilirubin occurring in 3% v 2 % on placebo.

1.6 Androgen deprivation therapy

Standard androgen deprivation therapy is a broad term encompassing any agent, or method, which invokes a castrate state for the treatment of prostate cancer. Medical therapy generally includes a gonadotropin releasing hormone (GnRH) analogue (agonist or antagonist) with a lowering of testosterone to castrate levels as the primary result of treatment. The agonists bind to the GnRH receptors in the pituitary to alter release of luteinizing and follicle stimulating hormones (LH and FSH) and eventually alter the feedback loop. A GnRH antagonist suppresses testosterone while avoiding the initial flare in testosterone seen with the administration of GnRH agonist. Examples of currently available formulations include: degarelix, goserelin, leuprolide, triptorelin, and histerelin. Surgical castration by means of an orchiectomy also reduces overall testosterone production. Hormone therapy is palliative in nature but has been shown to have a significant effect on the morbidity and mortality of prostate cancer. Notable side effects include sexual dysfunction, osteoporosis, sarcopenic obesity, increase in cardiovascular risk factors and diabetes, vasomotor symptoms, fatigue and alterations in cognition.

1.7 Nonclinical Experience

1.7.1 Drug Metabolism and Pharmacokinetics

Enzalutamide alters the functioning of the androgen receptor-signaling pathway. Enzalutamide has been shown to competitively inhibit androgen binding to androgen receptors and to inhibit the translocation of the receptor to the nucleus and subsequent DNA binding. The phase I, first-in-human trial of enzalutamide (or MDV3100) enrolled 140 patients with CRPC ³⁴. Dosing ranged from 30 to 600 milligrams (mg)/day with the maximum tolerated dose (MTD) determined as 240 mg orally per day. The recommended phase II dose was 160 mg/day.

The major active metabolite of enzalutamide is N-desmethyl enzalutamide. The pharmacokinetics of enzalutamide and this metabolite have been evaluated in healthy male volunteers or men with castrate-resistant metastatic prostate cancer ³³. A linear two-compartment model with first-order absorption adequately described. Following oral administration, the median time to reach maximum plasma enzalutamide concentrations (C_{max}) is 1 hour. The mean steady state C_{max} values are 16.6 μ g/mL for enzalutamide and 12.7 μ g/mL for N-desmethyl enzalutamide. The mean predose trough values are 11.4 μ g/mL and 13.0 μ g/mL, respectively. With the approved dosing schedule, steady state is reached in 28 days due to the long half-life ($t_{1/2}$) of 5.8 days. At steady state, enzalutamide showed approximately dose proportional pharmacokinetics. The mean apparent volume of distribution (V/F) of enzalutamide in patients after a single oral dose is 110 L. Enzalutamide is 98% bound to plasma proteins. N-desmethyl enzalutamide is 95% bound to plasma proteins.

Plasma samples were analyzed after a single oral administration of 160mg of carbon-labeled enzalutamide. Enzalutamide, N-desmethyl enzalutamide, and an inactive carboxylic acid metabolite accounted for 30%, 49%, and 10%, respectively, of the total AUC. Based on *in vivo* and *in vitro* data, CYP2C8 is primarily responsible for the formation of N-desmethyl enzalutamide, but *in vitro* data suggests the CYP3A4 is partially responsible for metabolism.

Enzalutamide is primarily eliminated by hepatic metabolism. The majority of elimination is through the urine (71% from one study) with 14% through feces. The mean apparent clearance (CL/F) of enzalutamide in patients after a single oral dose is 0.56 L/hour.

Based on limited data, the apparent clearance of enzalutamide is similar in patients with pre-existing mild and moderate renal impairment (CrCL 30 to < 90 mL/minute) compared to patients and volunteers with normal renal function. There are insufficient data to describe the potential effect of more severely impaired renal function on the clearance of enzalutamide. Hepatic function abnormalities of mild or moderate grade do not affect the area under the curve (AUC) of enzalutamide or its active metabolite.

1.8 Toxicology

1.8.1 Drug-Drug Interaction Risk Assessment

In a drug-drug interaction trial in healthy volunteers, a single 160 mg oral dose of enzalutamide was administered alone or after multiple oral doses of a strong CYP2C8 inhibitor and the AUC was increased 2.2 times with minimal effect on C_{max} . When administered with a single dose of a strong CYP3A4 inhibitor, the $AUC_{0-\infty}$ increased by 1.3 times ³³.

2. STUDY OBJECTIVES

2.1 Primary Objectives

To determine the incidence of metabolic syndrome within 12 months, as defined by the Adult Treatment Panel III, in patients treated with enzalutamide compared to standard androgen deprivation therapy.

2.2 Secondary Objectives

In patients treated with enzalutamide versus traditional ADT:

- To determine the incidence of metabolic syndrome within 6 months, as defined by the Adult Treatment Panel III, in patients treated with enzalutamide compared to standard androgen deprivation therapy
- To assess bone health, as measured by a DXA scanner
- To assess body composition (sarcopenic obesity), as measured by measurements of fat on CT
- To assess QOL, as measured by the FACT-P and SHIM
- To assess time to PSA progression and time to radiographic progression. Progression will be defined as lack of clinical benefit in the setting of either rising PSA, growth of visceral or soft tissue metastasis, or development of new bone metastasis as defined per protocol
- To assess the incidence of developing individual risk factors, or components, which comprise metabolic syndrome
- To assess the change in hs-CRP as a marker of inflammation
- To assess the safety and tolerance of enzalutamide or ADT
- To assess the change in physical function as measured by the Short Physical Performance Battery (SPPB)

3. STUDY ENDPOINTS

3.1 Primary Endpoints

Incidence of metabolic syndrome within 12 months as defined by the ATP III, in patients treated with enzalutamide versus patients treated with standard testosterone-lowering ADT.

3.2 Secondary Endpoints

- Incidence of metabolic syndrome within 6 months, as defined by the ATP III, in patients treated with enzalutamide versus patients treated with standard testosterone-lowering ADT
- Change in bone density, as measured by a DXA scanner
- Change in bone turnover as measured by bone-specific alkaline phosphatase and N-telopeptide
- Change in body composition (fat distribution as measured on CT)
- Change in QOL, as measured by the FACT-P and SHIM
- Time to PSA progression and time to radiographic progression. Progression will be defined as lack of clinical benefit in the setting of either rising PSA, growth of visceral or soft tissue metastasis, or development of new bone metastasis as defined per protocol
- Incidence of developing individual risk factors, or components, which comprise metabolic syndrome
- Change in inflammatory markers as measured by serum hs-CRP

- Safety and tolerability as assessed by regular recording of toxicities via physical exam and laboratory analysis using the CTCAE v4.1 guidelines
- Change in physical function as measured by the Short Physical Performance Battery

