4.4.2 Clinical Benefit

Continuation on the trial is dependent on toxicities, as well as evidence of clinical benefit. Patients must not have evidence of radiographic or PSA disease progression as per protocol section 7. Efficacy assessments will be performed via provider assessment. Imaging studies will be obtained every 6 months, or sooner at the discretion of the treating provider. PSA values will be assessed every 3

months, or sooner at the discretion of the treating provider. Patients with progressive disease per section 7 will be ineligible to receive further study treatment.

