7.2 Efficacy Evaluations

7.2.1 PSA

Patients will be monitored for clinical efficacy while on study. Serum PSA will be obtained every 3 months. PSA rise is allowable at the discretion of the investigator. However, patients must discontinue treatment if there is evidence of PSA progression as defined by an increase in $\geq 50\%$ from nadir and an absolute increase of at least 2 ng/mL above the nadir, occurring at least 12 weeks after start of therapy that is confirmed by two consecutive increases taken at least 2 weeks apart. The date of first recorded increase will serve as the date of progression.

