10.1.1 Endpoint Analysis

Primary endpoint

Metabolic syndrome incidence will be summarized by the proportion of patients with at least 3 of the 5 pre-specified criteria within the first 12 months of therapy.

Secondary endpoint

The secondary endpoints will be presented as follows:

Metabolic syndrome incidence will be summarized by the proportion of patients acquiring with at least 3 of the 5 pre-specified criteria within the first 6 months of therapy.

The change in bone turnover markers from baseline will be assessed for each treatment group. Measurements will be taken at day 1 of each cycle and reported as a continuous variable. A paired t-test will test within an arm as to whether the change from baseline to each time point is significantly different from zero.

The change in bone density, free fat mass, and fat mass will be measured at baseline, 3 months and 12 months and assessed for each treatment group. A paired t-test will test within an arm as to whether the change from baseline to each time point is significantly different from zero.

The change in QOL scores as measured by the FACT-P and SHIM at each visit, will be assessed in each treatment group.

Median time to PSA progression as defined in section 7.2. Time to PSA progression is defined as the time from randomization to the earliest objective evidence of PSA progression as defined per

protocol. If a patient has had a decline in PSA while on study, the PSA progression date is defined as the time from documented PSA nadir to an increase in PSA with confirmation as defined by protocol. Time to radiographic progression is defined as the time from randomization to the earliest objective evidence of radiographic progression as defined per protocol. Patients will be monitored at regular intervals for PSA change and radiographic change. Log rank test will be used to compare the distributions of above variables between the group treated with enzalutamide to the group on standard ADT.

The change in markers of inflammation as measured by circulating hs-CRP will be obtained at the beginning of each cycle.

Adverse events data will be summarized using tables and descriptive statistics.

The change in SPPB from baseline to 12 months will be measured as a continuous outcome. A clinically relevant change is a change in total score of 1, with a standard deviation at baseline of 1.5⁴².

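### The endpoint section gives both progression times one shared rule requiring loss of clinical benefit, while 7.2 and 10.1.1 define two separate endpoints by objective criteria

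*Combined protocol and SAP*

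**What the plan says.** Section 3.2 lists the two times together and defines them together: "Progression will be defined as lack of clinical benefit in the setting of either rising PSA, growth of visceral or soft tissue metastasis, or development". The last trigger reads in full "development of new bone metastasis as defined per protocol". The Protocol Summary and 2.2 carry the same sentence.

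Section 7.2.1 defines PSA progression by a rise of at least 50% from nadir together with "an absolute increase of at least 2 ng/mL above the nadir, occurring at least 12 weeks after start of therapy", confirmed by further increases. It separates this from a lesser rise: "PSA rise is allowable at the discretion of the investigator". Section 7.2.2 defines radiographic progression by RECIST v1.1 for soft tissue and by new lesions on bone scan for bone. Neither mentions clinical benefit.

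Section 10.1.1 refers to 7.2 for PSA progression and times it as "the time from randomization to the earliest objective evidence of PSA progression". It defines time to radiographic progression separately, again from randomization to the earliest objective evidence, and compares the arms by log-rank test. It adds that, after a PSA decline on study, the PSA progression date is an interval counted from the nadir.

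Section 4.4.2 is headed Clinical Benefit but does not define the term. It makes continuation depend on benefit, requires that there be no section 7 progression, and states: "Efficacy assessments will be performed via provider assessment".

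**The concern.** The section that should fix what the endpoints are differs in two ways from the sections that say how to derive and test them. It adds a condition, loss of clinical benefit, that the derivation rules lack. It also joins PSA and imaging triggers by an either/or and applies the result to both times, so two endpoints become one composite.

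The trial is open label, so a provider's view of benefit is formed with knowledge of the arm. If the 3.2 rule were used, event status in a between-arm comparison would rest on an undefined, unblinded judgement. This matters most for men with biochemically recurrent disease, whom 4.1 includes and whose progression may show in PSA alone.

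**Working it through.** **Design figure.** The plan states no event rate, power or other figure for the progression endpoints. Its only computed design figure is in 10.1: 28 per arm, 7% versus 32% metabolic syndrome, 80% power, actual alpha 0.054. Exact enumeration of the one-sided pooled chi-square test without continuity correction gives power 0.811 and alpha 0.0538 at the mean rate (0.07 + 0.32)/2 = 0.195, so the figure reproduces. No progression quantity enters it.

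**Both sets of rules applied to three hypothetical men** (all values assumed):

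- A: PSA nadir 1 ng/mL, then 3.5, 4.5 and 5.5 at weeks 26, 28 and 30; no new lesions; judged still to benefit. The rise is 3.5 − 1 = 2.5 ng/mL (at least 2) and 2.5/1 = 250% (at least 50%). It comes after week 12 and is followed by two further increases 2 weeks apart, so 7.2.1 is met.
- B: flat PSA; two new bone lesions seen after the 6-month assessment, when 7.2.2 needs no confirmatory scan; judged to have lost benefit.
- C: PSA nadir 1, then 1.6 and 1.9; no new lesions; judged to have lost benefit. The rise is 1.9 − 1 = 0.9 ng/mL, below 2, so 7.2.1 is not met.

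| Man | PSA time, 7.2.1/10.1.1 | Radiographic time, 7.2.2/10.1.1 | Shared rule in 3.2, read literally |
|---|---|---|---|
| A | event | no event | not met |
| B | no event | event | met, for both times |
| C | no event | no event | met |

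**Can the text be reconciled?** Three lenient readings are available.

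1. The closing reference to protocol definitions governs all three triggers, not only bone metastasis. Rising PSA then means 7.2.1 progression and C is no longer discordant. A and B are unchanged.
2. Loss of benefit simply means section 7 progression, as 4.4.2 might suggest. A then agrees. But 4.2 lists ongoing benefit beside stable disease, and 7.8 lists it beside absence of progression, in each case as a further condition.
3. The triggers are to be sorted, PSA to the PSA time and imaging to the radiographic time. B then agrees. The sentence does not say this.

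Only if all three are granted does 3.2 reduce to 7.2. The first alone leaves A and B; the first two leave B.

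**Size.** If a fraction q of men meeting 7.2.1 are judged still to benefit, the shared rule drops q of those PSA events and keeps 1 − q. The documents give no q, so the range is 0 to 1. Men like B add PSA events, so the net change can go either way.

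**Time origin within 10.1.1.** Treat start of therapy as randomization and let man A's nadir fall at week w. His PSA progression date is week 26, the first recorded increase under 7.2.1. Time from randomization is 26 weeks; time from nadir is 26 − w weeks. A fix that only points to 10.1.1 would carry this second conflict along.

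**The case against.** The strongest reply is that 10.1.1 already settles the matter. It is where the log-rank test is specified, it defines the two times separately, it asks for objective evidence, and it names 7.2 for PSA. A programmer works from that section, not from an endpoint bullet. The 3.2 sentence itself closes by pointing to protocol definitions, and 4.4.2 ties benefit to section 7. The 4.2 and 7.8 texts concern staying on treatment, not deriving endpoints.

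Much of this stands. The analyst would probably follow the objective rules, and man C is discordant only if the closing reference is confined to bone metastasis. Two things remain. The lenient readings do not remove the benefit condition and the either/or unless each is granted in turn. And for radiographic progression 10.1.1 gives no section number, only a reference to the protocol, of which 3.2 is part.

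A reader might go further and infer that discordant men would be censored, or that the log-rank comparison is shown to be biased by some multiple. The documents support neither. No censoring rule is written for these endpoints, so the most that can be said is that such a man is not an event. Any split by arm in how often benefit is judged to persist would be an invented figure.

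**Conclusion.** The conflict is real and limited. The Protocol Summary, 2.2 and 3.2 state a progression rule that differs from 7.2.1, 7.2.2 and 10.1.1, in that it requires an undefined, unblinded judgement and merges two endpoints. Men A and B show that event status can differ in both directions, given a literal reading and the assumed values.

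It would be tempting to conclude that the planned log-rank tests will be run on the wrong events. That does not follow, since 10.1.1 carries the objective definitions. The effect on those tests cannot be computed, because the documents give neither event rates nor a rate of disagreement. The endpoints concerned are secondary; the metabolic syndrome endpoint and the 28 per arm do not change. The correction is still worth making, because the endpoint section should not contradict the analysis it introduces.

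**What to change.** For endpoint derivation only, replace the shared sentence in the Protocol Summary, 2.2 and 3.2 with: PSA progression as defined in 7.2.1; radiographic progression as defined in 7.2.2; each analysed separately as in 10.1.1.

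In 10.1.1, time both endpoints from randomization, cite 7.2.2 by number for radiographic progression, and reconcile the sentence that counts PSA progression from nadir, so that the nadir serves only as the reference value for the PSA rise.

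Leave the treatment-continuation text in 4.4.2 as it is; it concerns patient management and need not enter endpoint derivation.

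The cost is wording in four places. It needs no new data and no change to visits or sample size.
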